6.5.2 Sensitivity Analysis

In cases where the plasma concentrations cannot be background-corrected in two or more subjects in a sequence, a sensitivity analysis will be performed similarly to the main analysis, whereby:

- If the subject's terminal elimination rate cannot be estimated it will be substituted by the average terminal elimination rate of the subjects having the same sex,
- If the uncorrected nicotine concentration at baseline is not available for the period 2 or 3, it will be substituted by the extrapolation of the previous concentrations using the terminal elimination rate.

6.5.3 Supplementary Analysis

In case of any uncorrected nicotine concentration at T_0 [uC₀] greater than 25% of their uncorrected maximum value, a supplementary analysis of the endpoints will be performed similarly to the main analysis, whereby data of these subjects for this specific product use period will be excluded from the analysis.

7. PHARMACODYNAMIC EFFECTS (SUBJECTIVE EFFECTS AND RELATED BEHAVIORAL ASSESSMENTS)

7.1 Data Collection

7.1.1 Product Evaluation Scale

Product evaluation will be assessed via a subject self-reported outcome measure, the Product Evaluation Scale (PES) [2, 3].

Statistical Analysis Plan Number CA36095

This 21 items measure consists of 4 multi-item scales and 3 single-item scales, arising from an adaptation of the modified cigarette evaluation questionnaire (mCEQ) [2] to conform to rating oral tobacco products [3].

The questionnaire assesses the degree to which subjects experience the reinforcing effects by measuring:

- Product satisfaction (satisfying, tastes good, enjoy the product, enjoy the sensations in month), average of the item scores from questions 1, 2, 3, and 12.
- Psychological rewards (calms down, more awake, less irritable, helps concentrate, reduces hunger), average of the item scores from questions 4, 5, 6, 7, and 8.
- Aversion (dizziness, nausea, too much nicotine, bothersome side effects), average of the item scores from questions 9, 10, 16, and 18.
- Relief (relief craving, relief withdrawal symptoms, relief urge to smoke, enough nicotine, craving for a cigarette), average of the item scores from questions 11, 13, 14, 15, and 20.
- Easy to use (single-item assessment), item score from question 17.
- Comfortable using (single-item assessment), item score from question 19.
- Concerned about dependence (single-item assessment), item score from question 21.

Subjects will be asked to assess the items of the questionnaire on a 7-point scale, ranging from 1 = "not at all" to 7 = "extremely". Only item 20 is reversed (1 = "extremely", and 7 = "not at all").

For the purpose of this study, the comfortable using in public single-item was reworded to a hypothetical situation, given subjects will not use the product in public in this specific study setting.

Each PES subscale will be treated as a continuous variable. For each multi-item subscale, the score will be derived by averaging the individual non-missing item scores, if at least 50% are non-missing, otherwise, the subscale score will be set as missing. Higher scores indicate greater intensity on that scale.

On Day 1 to Day 3, PES will be collected at 1 hour \pm 5 minutes after T_{0M} and T_{0A} ,

7.1.2 VAS Craving Assessment

Cigarette craving will be assessed using a one-item self-reported craving VAS [4], asking subjects to rate craving for cigarettes (*How strong is your craving for cigarettes?*), on a 100 mm unipolar scale, ranging from 0 (no craving) to 100 (strong craving).

On Day 1 to Day 3, VAS craving assessment will be collected at: Within 15 minutes prior to T_0 , after T_0 at 5 minutes \pm 1 minute, 10 minutes \pm 1 minute, 15 minutes \pm 1 minute, 20 minutes \pm 1 minute, 25 minutes \pm 1 minute, 30 minutes \pm 1 minute, 35 minutes \pm 1 minute, 40 minutes \pm 1 minute, 1 hour \pm 5 minutes, 3 hours \pm 5 minutes, 6 hours \pm 5 minutes.

In addition, VAS-craving assessment averaged during the sequence's period (from T1 to T11) will also be calculated for each subject at each product use period and summarized using descriptive statistics, as those variables will be used as a covariate for the inferential

analysis for objective 4. The AUCs for to T1 to T11 will be computed and added to the descriptive statistics.

7.1.3 VAS Liking Assessment

Liking will be assessed using a one-item self-reported liking VAS, asking subjects to rate liking for product (At this moment, my liking for this product is:) on a 100 mm bipolar scale, ranging from 0 (strong disliking) to 100 (strong liking), with a neutral middle point, as recommended in the FDA guidance for industry on abuse liability assessment [5].

Similarly, overall liking will be assessed using a one-item self-reported liking VAS (Overall, my liking for this product is:) on a 100 mm bipolar scale, ranging from 0 (strong disliking) to 100 (strong liking), with a neutral middle point.

On Day 1 to Day 3, VAS liking assessment will be collected at: After T_0 at 5 minutes \pm 1 minute, 10 minutes \pm 1 minute, 15 minutes \pm 1 minute, 20 minutes \pm 1 minute, 25 minutes \pm 1 minute, 30 minutes \pm 1 minute, 35 minutes \pm 1 minute, 40 minutes \pm 1 minute, 1 hour \pm 5 minutes, 3 hours \pm 5 minutes, 6 hours \pm 5 minutes.

In addition, VAS-liking assessment averaged over the product use period (from T1 to T6) and during the sequence period (T1 to T9) will also be calculated for each subject at each product use period and summarized using descriptive statistics as those variables will be used as a covariate for the inferential analysis for objective 4. The AUCs for to T1 to T11 will be computed and added to the descriptive statistics.

Similarly, overall liking will be assessed using a one-item self-reported liking VAS (Overall, my liking for this product is:) on a 100 mm bipolar scale, ranging from 0 (strong disliking) to 100 (strong liking), with a neutral middle point.

On Day 1 to Day 3, VAS overall liking assessment will be collected at 3 hours \pm 5 minutes after T_{0M} and T_{0A} .

7.1.4 VAS Satisfaction

Satisfaction will be assessed using a one item self-reported satisfaction VAS, asking subjects to rate product satisfaction (*Is the product 'satisfying' right now?*) on a 100 mm unipolar scale, ranging from 0 (not at all) to 100 (extremely), as recommended by Vansickel [6] to meet current regulatory recommendations in human abuse liability of tobacco and nicotine products.

On Day 1 to Day 3, VAS satisfaction will be collected at: After T_0 at 5 minutes \pm 1 minute, 10 minutes \pm 1 minute, 15 minutes \pm 1 minute, 20 minutes \pm 1 minute, 25 minutes \pm 1 minute, 30 minutes \pm 1 minute, 35 minutes \pm 1 minute, 40 minutes \pm 1 minute, 1 hour \pm 5 minutes, 3 hours \pm 5 minutes, 6 hours \pm 5 minutes.

In addition, VAS product satisfaction assessment during the sequence's period (from T1 to T11) will also be calculated for each subject at each product use period and summarized using descriptive statistics as those variables will be used as a covariate for the inferential analysis for objective 4. The AUCs for to T1 to T11 will be computed and added to the descriptive statistics.

7.1.5 VAS Intention to Use Again

Intention to use again will be assessed using a one-item self-reported VAS, asking subjects to rate intention to use product again (*How likely are you to use this product again*) on a 100 mm bipolar scale, ranging from 0 (very unlikely) to 100 (very likely), with a neutral

middle point.

On Day 1 to Day 3, VAS satisfaction will be collected at 30 minutes \pm 1 minute, and 3 hours \pm 5 minutes after T_{0M} and T_{0A} .

7.1.6 Sensory questionnaire

Sensory experience will be assessed with the sensory questionnaire which consists of 9 single items (strength of sensation in mouth, strength of sensation in throat, tingling sensation in gums, enjoyment of tingling sensation in gums, experience of dripping from the pouch, satisfaction with dripping, satisfaction with product duration, comfort with pouch size, and comfort with pouch against the gums) assessed on a 7-point scale, ranging from 1 = "not at all" to 7 = "extremely".

Each item will be analyzed individually, no total score will be computed on the Sensory questionnaire.

This questionnaire was developed internally by PMP S.A. based on consumer qualitative insights conducted with users of nicotine pouches in PMP S.A. consumer research studies.

On Day 1 to Day 3, the Sensory questionnaire will be conducted at 1 hour \pm 5 minutes after T_{0M} and T_{0A} ,

7.2 Data Summarization

Descriptive statistics (n, mean, SD, CV%, SEM, minimum, Q1, median, Q3, maximum, and 95% CI of mean) of the PES questionnaire including the subscale scores, VAS craving assessment, VAS liking assessment, VAS overall liking assessment, VAS satisfaction, VAS intent-to-use again, and sensory questionnaire will be provided by study product and assessment time point, when applicable. Change from baseline (pre-product use) for VAS craving score will be summarized by study product and assessment time point. Individual responses will be listed. AUCs for from T1 to T11 for VAS craving assessment, VAS liking assessment and VAS satisfaction assessment will be computed and displayed in summary tables. Summaries will be further stratified by sex.

7.3 Inferential Analysis

An analysis of covariance (ANCOVA) will be conducted by product use. The PK parameters (C_{max} , T_{max} , AUC_{infinity}, as applicable) will be transformed (except for the T_{max}) in the natural logarithmic scale. The model will include terms for sequence, period and the PD parameters mentioned in the Objective 4. The effect of VAS score will be analyzed in different models with:

- VAS-liking "in the moment" averaged over the product use period (from T1 to T6)
- VAS-liking "in the moment" averaged during the sequence period (T1 to T9)

Statistical Analysis Plan Number CA36095

- VAS product satisfaction "in the moment" during the sequence's period (from T1 to T11)
- VAS-craving averaged during the sequence's period (from T1 to T11)
- PES
- Sensory questionnaire

The results of this analysis will be presented by product in terms of:

- The percentage of variance explained by the PD parameter
- The standardized effect of the PD parameter, defined as the mean effect divided by the square root of its variance.

The ANCOVA analysis will be performed using the following SAS code:

PROC MIXED data=<> method=type3;

By product;

class sequence period;

model log(PK parameter) = sequence period score/ddfm=KR solution;

run;

A multivariate analysis to analyze the marginal effect of nicotine concentration, pH and moisture of NP 1.0 products will be performed. This analysis will be done using only NP 1.0 data. The PK parameters will be transformed in the natural logarithmic scale. The model will include covariates encoded as low and high for nicotine concentration (3.6 mg = LOW and 8.4 mg = HIGH), PH level (8.0 = LOW and 9.0 = HIGH) and moisture percentage (15% = LOW and 30% = HIGH).

The results of this analysis will be presented by product in terms of:

- The percentage of variance explained by the covariates (nicotine concentration, pH level and moisture)
- The standardized effect of the covariates (nicotine concentration, pH level and moisture) defined as the mean effect divided by the square root of its variance.

The multivariate analysis will be performed using the following SAS code:

PROC MIXED data=<> method=type3;

By product;

Class Nicotine concentration PH Moisture

model log(PK parameter) = Nicotine_concentration PH Moisture/ddfm=KR solution; run;

Another ANCOVA will be conducted similarly to the above with the exception that it will be performed overall using mixed effects ANCOVA where the model will include, in addition, the subject as a categorical random effect to model the within subject correlations.

The ANCOVA analysis will be performed using the following SAS code:

PROC MIXED data=< > method=type3; By product sex; class subject sequence period; model log(PK parameter) = sequence period score/ddfm=KR solution; random subject; run;

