12.9.5 Determination of Sample Size and Power Consideration

The sample size is empirically based as there are no considerations for statistical hypothesis.

A total of 24 subjects is expected to be sufficient to obtain a precision of 15% or less on the NP-1: Velo-NP C_{max} ratio.

The precision has been determined using the following geometric coefficient of variation (GCV) and within subjects correlation assumptions for C_{max} :

- For all products the GCV of C_{max} is assumed to be 40%. [1]
- The correlation within subjects on log-transformed data is assumed to be 0.7. It has been derived as the correlation that would explain the width of the confidence interval of the C_{max} difference between the Zyn and Velo-NP product, as compared to the confidence interval of the C_{max} of Zyn-NP and Velo-NP product as described in [16].

The precision has been determined using 10,000 simulations performed with SAS®.

Confidentiality Statement

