3.1 STUDY DESIGN

This is a single-center, randomized, controlled, open-label, cross-over study in healthy smoking subjects to investigate the nicotine PK profiles of 4 variants of NP 1.0 compared to marketed Velo-NP and Zyn-NP. In addition, PD effects will be evaluated to provide further insights on NP 1.0 product acceptance and abuse liability. The study will be conducted with 6 product use periods and 6 sequences in a Williams design (cross-over).

A Screening Visit will be conducted within 21 days (Day -22 to Day -2) prior to Admission (Day -1) to the investigational site (Figure 1). Subjects will be screened against eligibility criteria.

Statistical Analysis Plan Number CA36095

Figure 1 Study Design

Qualified subjects will return to the investigational site for Day -1. Subjects should have fasted for at least 10 hours prior to the safety laboratory assessments. After confirmation of eligibility, subjects will be enrolled. All subjects that are not enrolled will be considered as screen failures.

On Day -1, enrolled subjects will perform a product test using NP-1 for 30 minutes (\pm 1 minute). After the product test, subjects not willing and/or not ready to use NP 1.0 during the study will be discontinued from the study, will enter the 3-day Safety follow-up period, and will be replaced.

Subjects willing and ready to use NP 1.0, Velo-NP and Zyn-NP during the study after product test will start their exposure period of 3 days.

Twenty-four (24) subjects will be randomized to 1 of 6 possible sequences of product use on Day 1 to Day 3 with at least 25% of each sex (see Figure 1). The randomization process including the randomization sequences will be documented in the randomization plan.

On Day 1 to Day 3, after at least 8 hours of abstinence from any nicotine/tobacco containing products (nicotine wash-out), subjects will use one NP for 30 minutes (± 1 minute) according to randomized product use sequence in the morning and in the afternoon, by placing the NP between the upper lip and gum. Subjects will complete self-reported assessments of product evaluation, craving, liking, satisfaction, and intent to use again.

The start of the 30 minutes use period will be defined as T₀. T₀ in the morning (T_{0M}) and in the afternoon (T_{0A}) on Day 1 to Day 3 should be approximately at the same time, within a window of \pm 30 minutes. Venous blood samples will be obtained according to the standard operating procedures (SOPs) at the investigational site.

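### The reported *standardized effect* is an estimate divided by its standard error: a t statistic that grows with sample size, not a measure of strength of association

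*SAP*

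**What the plan says.** Objective 4 is to describe associations between PK and PD parameters. SAP 7.3 fits, for each product, "model log(PK parameter) = sequence period score/ddfm=KR solution", where the score is one PD measure. It then lists two results: "The percentage of variance explained by the PD parameter" and "The standardized effect of the PD parameter, defined as the mean effect divided by the square root of its variance". Protocol 12.6.2.3 gives the same two.

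The definition is used again in SAP 7.3 for the model of nicotine content, pH and moisture, where each covariate's effect is "defined as the mean effect divided by the square root of its variance". For that model Protocol 12.6.2.3 instead promises regression coefficients with confidence intervals.

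A further ANCOVA, with a random subject effect, is to be "performed overall using mixed effects ANCOVA". The code printed under it, however, carries a BY statement for product and sex.

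Protocol 12.9.4 says that any inference will give a point estimate and a 95% CI. The reporting lists in SAP 7.3 name neither a slope nor an interval. SAP 9 does not mention a change of reporting for these models and states that everything it does not list agrees with the protocol.

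**The concern.** The square root of the variance of an estimated effect is its standard error. Dividing the estimate by it gives the t value that the SOLUTION option already prints. A t value measures evidence against zero and mixes strength of association with amount of data. An objective that is purely descriptive, with no hypothesis to test, needs the strength.

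The plan places this quantity in fits that can differ in size: one product at a time, one product within one sex, and possibly all products together. A reader who compares columns headed *standardized effect* across those tables would partly be reading off the number of records.

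**Working it through.** **The plan's own figure.** The documents give no expected PK–PD correlation. The only design figure is a precision of 15% or less for the NP-1:Velo-NP Cmax ratio (Protocol 12.9.5: GCV 40%, within-subject correlation 0.7, 24 subjects). It reproduces: log SD = √ln(1 + 0.40²) = 0.385; SE = 0.385 × √(2 × 0.3/24) = 0.061; the 95% half-width on 110 df is 0.121, or 12.8%. Nothing below depends on it.

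**Identity.** For a slope b, b/√Var(b) = b/SE(b) = t. With partial correlation r, t = r × √(df/(1 − r²)). At fixed r it is proportional to √df.

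**Degrees of freedom.**
- *By product.* SAP 3.1: "Twenty-four (24) subjects will be randomized to 1 of 6 possible sequences of product use on Day 1 to Day 3", so at most 24 records per product. In a 6 × 6 Williams design the sequence fixes the period in which a given product is used, so sequence and period together have rank 6, not 11 (checked numerically). With one slope, df = 24 − 6 − 1 = 17.
- *Overall, if pooled.* Six uses × 24 subjects = 144 records. Removing 24 for subjects, 5 for periods and 5 for products leaves 110. The SAP's overall model has no product term; 144 − 24 − 5 − 1 = 114 would then apply. I use 110.
- *By product and sex, as coded.* Each sex makes up at least 25%, so 6 to 18 of the 24. Eighteen records leave 18 − 7 = 11 df and twelve leave 5. Six records spread over all six sequences leave none for seven parameters.

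**Results, with r assumed.**

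| Fit | df | t at r = 0.3 | t at r = 0.5 |
|---|---|---|---|
| One product, 12 of one sex | 5 | 0.70 | 1.29 |
| One product, all subjects | 17 | 1.30 | 2.38 |
| Pooled over products | 110 | 3.30 | 6.06 |

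The last two rows differ by √(110/17) = 2.5 whatever r is (2.6 with 114 df).

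**Simulation check.** 3,000 ordinary least-squares fits per setting were run with six sequence means and one slope. Records were treated as independent, so this checks the growth and does not imitate the mixed model. At r = 0.3 the mean t was 1.39 with 24 records, 2.08 with 48, 3.02 with 96 and 3.74 with 144. The slope scaled by SD(PD)/SD(log PK) averaged 0.295, 0.299, 0.300 and 0.301.

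**Missing data within one product.** Losing 2 of 24 records changes t by √(17/15) = 1.06; losing 4, by √(17/13) = 1.14.

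**Two-level factors.** Among the four variants nicotine splits 2/2, while pH and moisture each split 1/3. The predictor SDs are √(0.5 × 0.5) = 0.50 and √(0.25 × 0.75) = 0.43. An SD-scaled slope would thus shrink pH and moisture by about 13% relative to nicotine, purely through the choice of variants.

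**The case against.** The strongest reply is that an effect-size measure already stands beside the ratio. If the percentage of variance explained is a partial R², it equals t²/(t² + df), which is 9% at r = 0.3 for any df, and the t value adds only the sign. This stands, and it reduces the matter largely to a misleading label. It does not remove it: variance explained has no direction, no interval is listed for it, and it does not correct the column next to it. Sample estimates of it are also biased upwards in small fits (simulated mean 13.4% with 24 records and 9.7% with 144, at a true 9%).

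Second, the 2.5-fold contrast needs a pooled model, and the printed code does not fit one. That stands too. Equal strength in both fits is also a device for illustration: the by-product slope is between subjects, while a pooled slope mixes within- and between-subject information.

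Third, *its variance* might mean the variance of the PD score. The ratio would then be slope/SD(PD), which does not grow with sample size. But standardizing multiplies by that SD, so this reading needs a correction as well. A residual SD may have been intended; the text does not say so.

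Fourth, the slope and its interval are arguably covered by Protocol 12.9.4 and obtainable from the SOLUTION output. That is fair, but the SAP's reporting lists leave them out.

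A reader might infer that the study report will show overall associations 2.5 times too strong, or that products with a few missing periods cannot be compared at all. The documents support neither. The first depends on which version of the overall model is run and ignores the variance explained. For the second, the shift is about 6% to 14% for two to four lost records.

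**Conclusion.** The point holds as a defect of definition and labelling. On the natural reading of both documents, the *standardized effect* is a t statistic. It does not describe strength of association, and it is not comparable between fits with different residual degrees of freedom. The size is about 1.3 against 3.3 for the by-product and pooled fits. The individual values rest on an assumed partial correlation of 0.3; the ratio of about 2.5 does not, but it rests on pooling and on equal strength in the two fits.

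The consequence is confined to how Objective 4 and the product-factor model are reported. The main PK comparisons are untouched, and no hypothesis test is affected. The change is worth making because it costs almost nothing and restores outputs that the protocol already commits to.

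**What to change.** In SAP 7.3:

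1. **PD ANCOVAs.** List the slope with its 95% CI as the reported result, in line with Protocol 12.9.4. If a standardized measure is wanted, add either slope × SD(PD score)/SD(PK parameter on its analysis scale: log for Cmax and AUC, untransformed for Tmax) or the partial correlation. State that in a pooled fit these SDs include differences between products, so the scaled slope is not automatically comparable with the by-product values either.
2. **Label.** If estimate/SE is kept, call it a t statistic and print its degrees of freedom.
3. **Nicotine, pH and moisture.** Do not use an SD-scaled slope. Restore the regression coefficients and confidence intervals of Protocol 12.6.2.3, back-transformed to geometric mean ratios (high versus low) for log-scale parameters. The code printed for this model also runs by product, where each factor is constant; that statement must go before any coefficient can be estimated.
4. **Overall ANCOVA.** Reconcile the prose with the BY statement in its code, so that the reader knows how many records each result rests on.
5. **SAP 9.** Record any departure from the protocol's reporting that remains.

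The cost is a few lines of SAP wording, small edits to code and table shells, and no new data.

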12.6.2.3 Supplementary Analysis

In case of any uncorrected nicotine concentration at T_0 [uC₀] greater than 25% of their uncorrected maximum value, a supplementary analysis of the endpoints will be performed similarly to the main analysis, whereby data of these subjects for this specific study day will be excluded from the analysis.

An analysis of covariance (ANCOVA) will be conducted by product use. The PK parameters will be transformed in the natural logarithmic scale. The model will include terms for sequence, period and a PD parameters mentioned in the objective 4. The results of this analysis will be presented by product in terms of:

- The percentage of variance explained by the PD parameter
- The standardized effect of the PD parameter, defined as the mean effect divided by the square root of its variance.

Another analysis of covariance (ANCOVA) will be conducted similarly at the exception that it will be performed overall using mixed effects ANCOVA where the model will include additionally the subject as a categorical random effect to model the within subject correlations.

A multivariate analysis will be performed to analyze the joint effect of nicotine concentration, PH and moisture. The PK parameters will be transformed in the natural logarithmic scale. The model will include be adjusted for product use, sequence, period, and covariates encoded as low and high for nicotine concentration, PH level and moisture percentage. The results of this analysis will be presented for all products. The output will contain regression coefficients and their confidence intervals for factors of interests. Further details will be provided in the SAP.

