6.3 Plasma Nicotine Pharmacokinetic Parameters

Nicotine PK parameters will be derived from background-corrected plasma nicotine concentration versus time data using a non-compartmental analysis (NCA) technique using appropriate and validated PK software (e.g., Phoenix WinNonlin version 8.1 or higher).

For nicotine concentrations below the LLOQ (BLQ) for the calculation of descriptive statistics of observed plasma nicotine concentrations:

- BLQ values before T0 will be imputed by LLOQ/2.
- BLQ values after the last quantifiable value are not included in the analysis (e.g., for the calculation of AUC).

• Any BLQ value (after T0 and before the last quantifiable value) would need to be queried* and, if confirmed, it will be imputed by LLOQ/2.

*The query will be triggered by data QC, and will query the bioanalytical laboratory. The information on the value queried and a summarized response from the bioanalytical laboratory will be part of the SDTM data (e.g. in the CO domain).

The number and percent of values below LLOQ or above ULOQ will be presented in each summary table.

To minimize the carry-over effect in the nicotine plasma PK parameters due to limited washout periods, the correction for background-concentration (baseline nicotine level obtained pre-use) will be applied to the concentration data. This correction will be implemented by calculating the nicotine exposure parameters using background-corrected concentration values as described below.

The nicotine terminal elimination rate constant λ_z (and $t_{1/2z}$) will be estimated including PK samples listed in Section 6.1 by using a linear regression on the log-transformed plasma nicotine concentration data. The regression analysis should contain data from at least 3 different time points in the terminal phase (including the last quantifiable concentration but excluding the concentration at T_{max}), consistent with the assessment of a straight line on the log-transformed scale. The nicotine plasma background-corrected PK parameters will be derived by performing the NCA on the background corrected concentrations.

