For the purposes of background-correction of the plasma concentrations post-baseline the following formula will be applied: $cC_t = C_t - C_0 \cdot *e^{-\lambda z \cdot t}$. Where, cC_t is the corrected concentration at each time point, C_t is the observed concentration at each time point, C_0 is the pre-use baseline concentration, λ_z is the Day 2 terminal elimination rate constant, t is the actual time since start of product use, and t is the actual time since the time of the pre-use baseline sample.

In particular, the following PK parameters will be derived from background-corrected nicotine levels following 30 minutes of product use:

C_{max}	Maximum background-corrected plasma concentration. C_{max} will be reported as long as there is at least one quantifiable concentration post T_0 .
T_{max}	Time to maximum background-corrected plasma nicotine concentration $C_{\text{\scriptsize max}}.$
AUC _{0-5min}	Area under the background-corrected plasma concentration-time curve from start of product use (T_0) to 5 minutes.
AUC _{0-10min}	Area under the background-corrected concentration-time curve from T0 to 10 minutes.
AUC _{0-15min}	Area under the background-corrected concentration-time curve from T0 to 15 minutes.
AUC _{0-20min}	Area under the background-corrected concentration-time curve from T0 to 20 minutes.

Statistical Analysis Plan Number CA36095

AUC _{0-25min}	Area under the background-corrected concentration-time curve from T0 to 25 minutes.
AUC _{0-30min}	Area under the background-corrected concentration-time curve from T0 to 30 minutes.
AUC _{0-35min}	Area under the background-corrected concentration-time curve from T0 to 35 minutes.
AUC _{0-40min}	Area under the background-corrected concentration-time curve from T0 to 40 minutes.
AUC _{0-1h}	Area under the background-corrected concentration-time curve from T0 to 1 hour.
AUC _{0-3h}	Area under the background-corrected concentration-time curve from T0 to 3 hours.
AUC _{0-6h}	Area under the background-corrected plasma nicotine concentration-time curve from T_0 to 6 hours.
$AUC_{0\text{-infinity}}$	Area under the background-corrected plasma nicotine concentration-time curve extrapolated from T0 to infinity.

All AUC parameters will be calculated using linear trapezoidal with linear interpolation method.

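### The Objective 4 craving models correct nicotine for its pre-use level but leave pre-use craving out, so the craving association can be diluted or confounded

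*SAP*

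**What the plan says.** **Nicotine.** SAP 6.3 says that "the correction for background-concentration (baseline nicotine level obtained pre-use) will be applied to the concentration data". The observed concentration is reduced by the pre-use concentration, decayed at the subject's terminal rate. Cmax, Tmax and all AUCs are derived from the corrected values.

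**Craving.** In SAP 7.3 the craving covariate is "VAS-craving averaged during the sequence's period (from T1 to T11"), a plain average of post-use ratings. Protocol 3.1 and SAP section 2 define the Objective 4 craving endpoint in the same way.

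**Models.** The by-product ANCOVA in SAP 7.3 is "model log(PK parameter) = sequence period score/ddfm=KR solution". Protocol 12.6.2.3 agrees: "The model will include terms for sequence, period and a PD parameters mentioned in the objective 4". The second ANCOVA in SAP 7.3 adds a random subject term. Its text calls it an overall analysis, but its code reads "By product sex; class subject sequence period". None of the three contains pre-use craving.

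**Pre-use craving.** It is available at every use. SAP 7.1.2 states that "VAS craving assessment will be collected at: Within 15 minutes prior to" T0. SAP 7.2 treats it as the baseline, in descriptive tables only: "Change from baseline (pre-product use) for VAS craving score will be summarized by study product and assessment time point". Protocol 12.1.2 defines a pre-T0 baseline for PD as well as PK analyses, but places it 5 minutes before T0. Neither document says why baseline craving is left out of the inferential models.

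**The concern.** Subjects smoke at least 10 cigarettes a day (Protocol 5.1.1), may use no other nicotine product from admission (6.6.1), and start each use after at least 8 hours of abstinence (6.2.2). Protocol 2.3.3 expects withdrawal symptoms, including urge to smoke. Subjects can therefore differ in craving before the pouch is placed, and nicotine absorbed after T0 cannot have caused those differences.

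The by-product fit has one record per subject, so these differences enter the score directly. One of the two outputs that SAP 7.3 reports is the percentage of variance explained by the PD parameter, which irrelevant variation in the score lowers. At stake is a weak reported link between exposure and craving where a stronger one exists or, if starting craving is related to absorption, a distorted one.

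Only the craving models are affected. Liking and satisfaction have no pre-use rating.

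**Working it through.** **The plan's own figure.** There is no design calculation for Objective 4. The only one, in Protocol 12.9.5, is a precision of 15% or less for the NP-1:Velo-NP Cmax ratio with 24 subjects, geometric CV 40% and within-subject correlation 0.7. It reproduces: log SD = sqrt(ln(1 + 0.40²)) = 0.385; SD of a paired difference = 0.385 × sqrt(2 × 0.3) = 0.298; SE = 0.298/sqrt(24) = 0.0609. The upper 95% half-width is 13.4% with t on 23 df and 12.7% with the normal quantile. This has no bearing on the craving models.

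**Inputs.** The model terms, the T1 to T11 average, n = 24 and six sequences come from the documents. Two quantities do not, and are assumed over a range:
- rb, the correlation of pre-use craving with mean post-use craving;
- rho, the correlation of log PK with the part of mean craving that pre-use craving does not explain.

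**Formula.** In standardised form, mean craving = rb × B + sqrt(1 - rb²) × e, with B the pre-use craving and e independent of B. Then

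corr(PK, mean craving) = rb × corr(PK, B) + sqrt(1 - rb²) × rho.

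If B is unrelated to PK, the first term is zero. The raw correlation is rho × sqrt(1 - rb²), and the variance explained is rho² × (1 - rb²). If B is related to PK, the first term adds to or offsets the second according to its sign.

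**Results for rho = -0.5, B unrelated to PK.** The last three columns are the proportion of simulated trials (3,000 per row, by-product model, 24 subjects) in which the 95% CI excludes zero.

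| rb | Share of craving variance from B (rb²) | Loss of correlation | Variance explained by raw score | Raw score | Baseline as covariate | Change score |
|---|---|---|---|---|---|---|
| 0 | 0% | 0% | 25% | 0.62 | 0.59 | 0.33 |
| 0.3 | 9% | 5% | 23% | 0.58 | 0.60 | 0.43 |
| 0.5 | 25% | 13% | 19% | 0.48 | 0.59 | 0.47 |
| 0.7 | 49% | 29% | 13% | 0.34 | 0.58 | 0.52 |
| 0.9 | 81% | 56% | 5% | 0.14 | 0.59 | 0.58 |

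With the covariate, the simulated correlation is about -0.49 at every rb.

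**Degrees of freedom.** In a six-period, six-sequence Williams square (SAP 3.1, Protocol 12.9.1) fitted by product, sequence determines period. An example square gave design rank 6 for every product. Residual df are 24 - 6 - 1 = 17 with the score, and 16 with baseline craving added.

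**Random subject term.** As coded, by product and sex, the second ANCOVA also has one record per subject in each run. The subject term cannot be separated from the residual, so it removes none of the between-subject difference in starting craving.

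**The case against.** **The endpoint is the raw average.** Protocol and SAP agree on it, the aim is descriptive, and PK background correction exists to deal with carry-over, which does not by itself oblige craving to be treated alike. This stands. A reader might infer that the SAP departs from the protocol; it does not, and the raw-average model should be kept.

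**Pre-use craving may matter little.** A reader might infer that it dominates the score. The documents give no VAS SD and no correlation between pre-use and post-use craving. The baseline share passes one half only when rb exceeds sqrt(0.5) = 0.71. A high rb is plausible, since nine of the eleven averaged ratings fall within the first hour, but it is not established.

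**Relief may depend on starting craving.** On a scale ending at no craving, relief cannot exceed the starting level. Take SD 20 for both pre-use craving and relief, correlated 0.5, with PK unrelated to pre-use craving. The raw correlation then equals the PK-relief correlation in size: 20/sqrt(400 + 400 - 400) = 1.00. This stands against using raw relief as the yardstick. It does not rescue the raw score against the covariate model: here rb = (400 - 200)/(20 × 20) = 0.5, so the raw correlation is still sqrt(0.75) = 0.87 of the adjusted one.

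**Morning and afternoon.** Mean differences between them are absorbed by sequence and period. The concern is confined to differences between subjects.

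**Sign reversal.** A reader might infer that the association could change sign. With rho = -0.5, the formula requires corr(PK, B) above 0.357/0.7 = 0.51 at rb = 0.7, or above 0.218/0.9 = 0.24 at rb = 0.9. At rb = 0.5 it requires more than 0.433/0.5 = 0.87, which is the largest value compatible with rho = -0.5. Nothing in the documents indicates such a relation, and a fixed 30-minute use without manipulating the pouch (Protocol 6.2.2) limits self-titration.

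**Low consequence.** Even with adjustment, the CI excludes zero in only about 59% of trials at rho = -0.5, and the study is exploratory (Protocol 12.9.4). This limits the weight of the point without removing it.

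**Conclusion.** The asymmetry is in the text of both documents: PK is corrected for its pre-use level, craving is not, and the baseline needed is collected before every use. The craving association can therefore be diluted, or confounded in either direction if pre-use craving is related to PK.

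The dilution runs from 5% of the correlation at rb = 0.3 to 56% at rb = 0.9. That range assumes pre-use craving is unrelated to PK, and it applies to the by-product fit; rb is not in the documents. The documents do not support saying that pre-use craving dominates the result or that the sign will reverse.

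This is a shared choice of protocol and SAP in an exploratory objective. The change is worthwhile because it is cheap: in the simulations the covariate model is about level with the raw score when baseline is irrelevant (0.59 against 0.62) and clearly better once rb reaches 0.5.

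**What to change.** In SAP 7.3, for the craving models only, both by-product and overall, add a model with the pre-use VAS craving of the same use as a covariate, with terms `sequence period VASC_pre score`. Report it beside the raw-average model, which remains the protocol endpoint.

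Do not use change from pre-use craving as a substitute. It forces the two coefficients to be equal and opposite, and it does worse than the raw score when rb is low (0.33 against 0.62 at rb = 0).

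State that the craving baseline is the rating taken within 15 minutes before T0, and reconcile this with the 5 minutes in Protocol 12.1.2. When adding the covariate to the second ANCOVA, also reconcile its text (overall) with its code (by product and sex).

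Record the addition in SAP section 9; Protocol 12.1 allows changes of method documented in the SAP and CSR. The cost is one residual df per by-product fit (17 to 16) and a few lines of SAP text. No new data are needed.
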